We will first develop, tailor, and refine *PrEP My Way* for use with young women in Kisumu, Kenya (Aim 1). We will use a client-centered, iterative approach, involving individual interviews and focus group discussions to optimally design the *PrEP My Way* kit (with instructional materials) and peer delivery system (including communication and kit delivery plans). We will then test the intervention for feasibility, acceptability, and preliminary impact on PrEP adherence and program retention (Aim 2). We will randomize up to 150 Kenyan women to *PrEP My Way* versus standard of care (i.e., clinic-based delivery of PrEP and sexual health services) and follow them for 6 months. Feasibility will be assessed by receipt of the kit at 1, 3, and 6 months and ability to use its components per protocol. Acceptability will be determined through a mixed-methods interview at 6 months. Preliminary impact will be evaluated by dried blood spot tenofovir levels (adherence) and kit use/clinic attendance at 6 months (retention) as primary outcomes. Mediators and moderators of PrEP use (e.g., empowerment and mental health) will be explored through questionnaires at baseline and 6 months.

Design: Formative work, followed by a pilot randomized controlled trial (RCT) of *PrEP My Way* versus standard of care (1:1)

Population: Young (16-24 years old) sexually active women who are interested in taking PrEP and own a phone

Study site: Kisumu, Kenya

Specific aims:

1. Develop *PrEP My Way*. Using a client-centered approach, we will iteratively conduct individual interviews and focus group discussions with up to 70 Kenyan women (age 16-24) or other relevant community members to optimally design *PrEP My Way* (the kit with instructional materials) and peer delivery system (including phone communication and kit delivery plans).
2. Assess *PrEP My Way* for feasibility, acceptability, and preliminary impact on PrEP adherence and program retention. We will randomize up to 150 Kenyan women (age 16-24) to *PrEP My Way* versus standard of care (i.e., clinic-based delivery of PrEP and sexual health services) and follow them for 6 months. Feasibility will be assessed by receipt of the kit at 1, 3, and 6 months and ability to use its components per protocol. Acceptability will be determined through a mixed-methods interview. Preliminary impact will be evaluated by dried blood spot tenofovir levels (adherence) and kit use/clinic attendance at 6 months (retention). Potential

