1. Develop PrEP My Way. Using a client-centered approach, we will iteratively conduct individual interviews and focus group discussions with up to 70 Kenyan women (age 16-24) or other relevant community members to optimally design *PrEP My Way* (the kit with instructional materials) and peer delivery system (including phone communication and kit delivery plans).
2. Assess PrEP My Way for feasibility, acceptability, and preliminary impact on PrEP adherence and program retention. We will randomize up to 150 Kenyan women (age 16-24) to *PrEP My Way* versus standard of care (i.e., clinic-based delivery of PrEP and sexual health services) and follow them for 6 months. Feasibility will be assessed by receipt of the kit at 1, 3, and 6 months and ability to use its components per protocol. Acceptability will be determined through a mixed-methods interview. Preliminary impact will be evaluated by dried blood spot tenofovir levels (adherence) and kit use/clinic attendance at 6 months (retention). Potential influencing and mediating socio-behavioral factors will be explored with questionnaires at 0 and 6 months.

Design and Methodology

Study setting. Both aims of this protocol will take place in Kisumu, Western Kenya. This area is largely rural with an urban center and a total population of ~1,000,000. HIV prevalence is 21% among women. This study will be run under the KEMRI Research Care and Training Program (RCTP, a comprehensive HIV prevention, care and treatment program working in 100 clinics in Western Kenya). The RCTP is staffed by clinicians, pharmacists, counselors, community outreach officers, and laboratory technicians who are trained to provide routine health services, including HIV testing, PrEP, STI testing and treatment, and contraception. It has supported several projects focused on young women, as well as family planning/HIV integration studies (e.g., MPYA, PrIYA).

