protections for human subjects in research; confidentiality of the study participants will be particularly emphasized. Peers will receive a stipend of 20,000 Kenyan Shillings (~\$200 US) per month, consistent with payment for peer/lay healthcare workers in other community-based health programs in the area. We will recruit three peers with each serving 15-20 participants. With the projected enrollment schedule over three months and the quarterly follow-up, this case load will amount to 8-16 clients per month, or 1 delivery every 1-2 work days (assuming ~20 work days per month). This workload is reasonable, even if multiple attempts are needed to successfully deliver the kit. Participants will have options for engaging with peers, ranging from none beyond kit delivery to step-by-step support in using each component of the kit and follow-up questions by phone.

We will document the training process for the peers to promote reproducibility in future studies and/or program implementation. We will also observe the quality of the peer's engagement with participants to document the content of their interactions, which can be accomplished during the planned time and motion studies (below).

Cost. Because intervention effectiveness is not the aim of this study, we will not perform a formal cost-effectiveness analysis. However, we will collect costing data on the components of the intervention and perform time and motion studies over two-week periods in both the intervention and control arms of the study mid-way through the study period (i.e., when procedures are running smoothly). Up to 20 client interactions will be observed in each setting to capture the range of time and extent of effort required for PrEP, contraception, and STI services. An RA may observe the peers working with participants in the community, or the peer may perform the observation herself (per the preference of the participant). No identifiers of specific clients in the clinic will be recorded. This data will be used to formulate a preliminary sense of the costs of the *PrEP My Way* intervention relative to standard of care.

Outcome measures

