Feasibility. Feasibility will be assessed by the following metrics: 1) receipt of the *PrEP My Way* kit at Months 1, 3, and 6, and 2) ability of the participant to use each aspect of the kit (i.e., the HIV self-test, use of the vaginal swab, and self-administration of medroxyprogesterone [if desired]) per protocol. The intervention will be considered feasible if $\geq 70\%$ (35/50) participants 1) receive a kit and 2) achieve a readable HIV test, usable vaginal swab, and self-injection of medroxyprogesterone, if desired, at $\geq 66\%$ (2/3) of visits.

Acceptability. The *PrEP My Way* intervention will be considered acceptable if $>70\%$ (35/50) participants rate 70% (7/10) items on the SUS as "very good" or higher. The qualitative interview will delve deeply into each of the four domains of the UTAUT model to provide in depth feedback on the intervention.

Primary outcomes- Preliminary impact on PrEP adherence and program retention at 6 months. PrEP adherence will be assessed primarily by DBS for tenofovir diphosphate (TFV-DP) concentration. The TFV-DP concentration will provide an estimate of doses taken over the prior 3 months (see Table 4; [11, 50]). Retention will be assessed by kit receipt in the intervention arm and clinic attendance per clinic records in the control arm at Month 6. Potential influencing and mediating socio-behavioral factors (Table 2) will be explored.

Secondary outcomes. We will assess the following:

Table 4. TFV-DP concentrations in DBS	
Estimated use	Median fmol/punch (IQR)

- Self-reported PrEP adherence at Months 1, 3, and 6 (intervention arm) and Month 6 (control arm). We will use the 3-item scale developed by Wilson et al, which involves different recall tasks (frequency, percent, and rating of adherence) over the prior 30 days [51]
- PrEP persistence over the 6-month period
- Rates of STI testing at Months 1, 3, and 6
- Rates of pregnancy test and contraception pick up at Months 1, 3, and 6
- Cost estimates

Protective*	>1,250
Moderate	900-1,249
Low	<900

*Exact value to be explored (see text)

Analysis

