Our power calculations are based on 80 participants, given an expected loss to follow-up of 20% (estimated from our current MPYA study). As shown in Figure 6, assuming a standard deviation of 10%, 80 participants will have limited power to detect a difference of 20% between the study arms (e.g., ~40% power if the primary outcome is seen in 40% of the control group versus 60% in the intervention group; see the circled green dot). If a stronger effect is seen (e.g., closer to the ideal target of 40%), we may achieve >80% power. We believe this sample size is appropriate for the development of the *PrEP My Way* intervention. If the intervention is also found to be feasible and acceptable, we look forward to fully testing the intervention in a subsequent, fully powered study.

[figure not shown]
Participant retention and withdrawal

Participants will be tracked primarily through peers (intervention) and the clinic visits (standard of care). Individuals missing scheduled appointments will be contacted through study retention teams. Participants will be able to withdraw from the study at any time.

Ethical Considerations

Human subjects

Figure 6. Estimate power for the study sample size

This study will involve young Kenyan women in two sets of study procedures to develop and preliminarily test the *PrEP My Way* intervention.

- Intervention development (Aim 1). We will use a client-centered approach, involving individual interviews and two focus group discussions with up to 25 Kenyan women to optimally design the *PrEP My Way* kit (with instructional materials) and peer delivery system (including communication and kit delivery plans).
- Pilot randomized controlled trial (Aim 2). We will randomize 150 Kenyan women to *PrEP My Way* versus standard of care (i.e., clinic-based delivery of PrEP and sexual health services) and follow them for 6 months. These participants will be distinct from those participating in the intervention development aspects of the study. Feasibility will be assessed by receipt of the kit at 1, 3, and 6 months and ability to use its components per protocol. Acceptability will be determined through a mixed-methods interview at 6 months. Preliminary impact will be evaluated by dried blood spot tenofovir levels (adherence) and kit use/clinic attendance at 6 months (retention) as primary outcomes. Mediators and moderators of PrEP use (e.g., empowerment and mental health) will be explored through questionnaires at baseline and 6 months.

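### The power text, success counts and peer caseload describe about 100 randomised women, but Human subjects says 150; separately, the acceptability count does not meet its own rule

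*Combined protocol and SAP*

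**What the plan says.** All places are in the combined protocol and SAP.

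- **Power.** "Our power calculations are based on 80 participants, given an expected loss to follow-up of 20" per cent. The section continues: "assuming a standard deviation of 10%, 80 participants will have limited power to detect a difference of 20% between the study arms". It gives power of about 40% for 40% in the control group against 60% in the intervention group, and more than 80% as the difference nears 40 points.
- **Human subjects, Aim 2 bullet.** "We will randomize 150 Kenyan women".
- **Opening summary, Specific aims, Specific Objectives and Aim 2 Overview.** "We will randomize up to 150 Kenyan women".
- **Outcome measures, Feasibility.** At least 70%, printed as ("35/50) participants 1) receive a kit and 2) achieve a readable HIV test", and so on).
- **Outcome measures, Acceptability.** More than 70%, printed as ("35/50) participants rate 70% (7/10) items on the SUS".
- **Peer identification and hiring, and oversight.** "We will recruit three peers with each serving 15-20 participants". The number three is repeated under Potential risks and protection against risk, in the item on loss of privacy through the kit.
- **Analysis, Primary outcomes.** Protective against non-protective TFV-DP, and retained against not, are compared by Chi-square tests. The same paragraph says that some of the shipped dried blood spots (DBS) will be assayed.

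**The concern.** Three planning elements (power, success counts, staffing) were set for one trial size, and the section on human subjects commits to one that is half as large again. Nowhere does the text state 100 as the planned number; the reader has to derive it from 80 and 20%. If 150 women are enrolled, the printed power, the printed counts and the workload that the protocol calls reasonable all belong to a smaller trial.

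The acceptability criterion has its own defect. A result of exactly 35 of 50 passes by the count and fails by the percentage rule. The Power section makes the later, fully powered trial depend on the intervention proving feasible and acceptable, so the threshold should have one reading.

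**Working it through.** **Inputs.** From Power: 80 evaluable, 20% loss, 40% v 60%, stated power about 40%. From Consent, enrollment, and randomization: 1:1 allocation. From Analysis: Chi-square test of two proportions. From Human subjects: 150 randomised. Alpha is not in the text; two-sided 0.05 is assumed.

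**1. Implied size.** 80/(1 − 0.20) = 100 randomised, 50 per arm, 40 per arm evaluable. For 150: 150 × 0.80 = 120, or 60 per arm evaluable.

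**2. The plan's own power figure.** With n per arm and p̄ = 0.50,

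power = Φ{[0.20 − 1.96 √(2 × 0.50 × 0.50/n)] / √[(0.40 × 0.60 + 0.60 × 0.40)/n]}.

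At n = 40: (0.20 − 1.96 × 0.1118)/0.1095 = −0.175, so power = 43.1%. Full enumeration gives 45.8% for the uncorrected Chi-square test and 36.9% with the Yates correction or Fisher's test. The stated 40% or so lies inside that range. For 40% v 80% the same method gives 96.8%, so the claim of more than 80% near the ideal target also holds.

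**3. Power if 150 are randomised.** At n = 60: (0.20 − 1.96 × 0.0913)/0.0894 = 0.236, so power = 59.3%.

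| Evaluable per arm | Normal approximation | Uncorrected Chi-square, enumerated | Yates or Fisher, enumerated | Difference from 40% with 80% power |
|---|---|---|---|---|
| 40 | 43.1% | 45.8% | 36.9% | 30.7 points |
| 60 | 59.3% | 61.2% | 54.0% | 25.3 points |

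The gap from the printed figure is 59 − 40 = about 19 points. It rests on 20% loss and on assay of every retained woman's DBS. If all 75 per arm were analysed, the normal approximation would give 69%.

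**4. Success counts.**
- At 50 women, 0.70 × 50 = 35. At least 70% needs 35; more than 70% needs 36 (72%). So 35/50 is right for feasibility and wrong for acceptability as written.
- At 75 women, 0.70 × 75 = 52.5. Both rules need 53 (70.7%), since 52/75 = 69.3%.
- The usability scale is collected only at Month 6. If the denominator were 60 respondents, 42/60 would be exactly 70%, so more than 70% would need 43.

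**5. Caseload.** 3 × 15 to 3 × 20 = 45-60 intervention women, or 90-120 randomised at 1:1. That range contains 100 and excludes 150. Per peer: 50/3 = 16.7, inside 15-20; 75/3 = 25, outside it.

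**6. The 10% standard deviation (minor).** The individual-level SD of a binary outcome at 40% or 60% is √0.24 = 0.49, so 10% cannot be that. The standard error of the difference at 40 per arm is √(2 × 0.24/40) = 0.11, which is one possible meaning. The stated power follows from the two proportions without it.

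**The case against.** The best defence is that the conflict comes down to one missing qualifier. Every other statement of sample size gives 150 as a ceiling, which 100 satisfies, and power, counts and caseload agree with one another. The Human subjects recap is loose elsewhere too: it gives up to 25 women for Aim 1, where Specific aims and Specific Objectives allow up to 70 women or other community members. All of that is fair, and it means the repair may be short. It does not remove the flat 150, and it leaves the planned number unstated.

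The consequences are also modest. Power printed too low is conservative, the protocol already calls its power limited, and the percentages rather than the counts govern success. These points stand.

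Several stronger readings are tempting and not supported:

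- A reader might infer that one cannot tell which trial the figures describe. One can: 80 after 20% loss, and denominators of 50, point to about 100. What is unclear is how many women will be enrolled.
- A reader might take 59% as the trial's true power. The documents do not secure it, because the Analysis section speaks of assaying some of the DBS. The same condition lies behind 80 evaluable women for adherence.
- A reader might fear that 35 would be accepted as success out of 75 (46.7%). The plan never applies 35 to 75.
- A reader might conclude that the 10% SD invalidates the power figure. It does not, and Figure 6, which is not shown here, may define it.

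A sign lost in PDF extraction could explain the strict inequality for acceptability. That cannot be excluded, so the sponsor should check the source file.

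**Conclusion.** The inconsistency is real and should be fixed. Power, counts and caseload describe about 100 randomised women, compatible with a ceiling of 150 but not with an unqualified 150. The stated power of about 40% is fair for 80 evaluable women (43%; 37-46% by enumeration). With 150 randomised, 20% lost and all retained women's DBS assayed, it would be about 59% (54-61% by enumeration), some 19 points above the printed value. The statement that power is limited for a 20-point difference survives at either size.

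Independently of sample size, the acceptability rule and its count disagree: by one woman at 50 per arm, where 36 rather than 35 is needed.

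The power figures assume a two-sided 0.05 test, 1:1 allocation and equal loss in the two arms.

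**What to change.** State one planned randomised number and carry it through.

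**If 100:** replace the flat 150 in Human subjects with the planned 100, and put that number beside the ceiling of 150 wherever the ceiling is kept. Keep power of about 40%, and keep 35/50 for feasibility.

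**If 150:**
- Restate power, for example: With 60 evaluable women per arm, a two-sided 0.05 Chi-square test has about 59% power for 40% v 60%, and 80% power for a difference of about 25 points from 40%.
- Say that this requires DBS assay for all retained women, and reconcile it with the statement in Analysis that some will be assayed.
- Print 53/75 for both criteria if the full arm is the denominator, as it is now; otherwise state the respondent denominator for the Month 6 usability scale.
- Reconcile the caseload text, and the mention of three peers in the privacy risk item, with 75 women. How to staff this is for the sponsor.

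**Either way:** make the acceptability sign and count agree. For 100 randomised, use more than 70% with 36/50, or at least 70% with 35/50. As minor clarifications, state alpha and what the 10% SD refers to, unless Figure 6 already does, and check that figure against the chosen number.

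The cost is wording, with no participants beyond the ceiling already permitted. Choosing 150 also means settling assay numbers and peer coverage.
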